### **5.4. Withdrawal/Stopping Criteria**

The following actions must be taken in relation to a subject who fails to attend the clinic for a required study visit:

- The site must attempt to contact the subject and re-schedule the missed visit as soon as possible.
- The site must counsel the subject on the importance of maintaining the assigned visit schedule and ascertain whether or not the subject wishes to and/or should continue in the study.
- In cases where the subject is deemed ‘lost to follow up’, the investigator or designee must make every effort to regain contact with the subject (where possible, 3 telephone calls and if necessary a certified letter to the subject’s last known mailing address or local equivalent methods). These contact attempts should be documented in the subject’s medical record.

- Should the subject continue to be unreachable, only then will he/she be considered to have withdrawn from the study with a primary reason of “Lost to Follow-up”.

Any subject that fails to achieve EULAR good/moderate response at Week 36 will not be dosed at Week 38, and will be withdrawn from the study; no further study treatment will be administered. A notification that the subject must be withdrawn will be sent to the investigator prior to the scheduled Week 38 visit.

A subject may withdraw from study treatment at any time at his/her own request, or may be withdrawn at any time at the discretion of the investigator for safety, behavioural or administrative reasons.

**In addition, study medications will be discontinued and the subject withdrawn from the study in the event of any of the following:**

- All serious infections.
- Pregnancy.
- Confirmed PAP.
- Severe or serious hypersensitivity reactions, including anaphylaxis.
- If the liver chemistry stopping criteria (Section 5.4.1) or QTc stopping criteria (Section 5.4.2) are met.
- Persistent or recurrent hematological laboratory abnormalities (see Section 5.5.2).
- Other serious or severe adverse events, at the discretion of the investigator, after consultation with the Medical Monitor.

If a subject withdraws from the study, he/she may request destruction of any samples taken, and the investigator must document this in the site study records.

[figure not shown]
Any subject who withdraws must complete an early withdrawal visit and the 12 week follow-up visit.

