## 2 STUDY OBJECTIVES AND ENDPOINTS

Objectives	Endpoints
Primary	
• To assess the efficacy of GSK3196165	• Proportion of subjects who achieve disease activity score for 28 different joints with CRP value (DAS28(CRP)) remission (DAS28 <2.6) at Week 24.
Secondary	
To assess 

• Dose-efficacy response of GSK3196165

• Safety

• Population pharmacokinetics

• Pharmacodynamics

• Novel biomarkers

○ To examine the molecular profiles of blood samples to identify factors that may influence biological and clinical responses to GSK3196165 and/or associated with the development or progression of RA or medically related conditions.

	Major Secondary Efficacy Endpoints 

• Change from baseline in DAS28(CRP) at Week 12 (to support dose response evaluation).

• Proportion of subjects achieving DAS28(CRP) remission at all assessment timepoints.

• Change from baseline in DAS28(CRP) at all assessment timepoints.

• Time to first DAS28(CRP) remission.

• Proportion of subjects achieving categorical DAS28(CRP) response (moderate/good EULAR response) at all assessment timepoints.

• ACR 20/50/70 response rates at all

Objectives	Endpoints

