#### 4.3.1 Analysis Datasets

For each of the efficacy evaluations of binary endpoints, subjects with missing efficacy data, early withdrawals, subjects who received more than 10 mg/day of prednisone equivalent oral corticosteroids, subjects with any new use of parenteral corticosteroids, more than one intra-articular corticosteroid injection within a 24 week period, or subjects who received rescue treatment will be imputed as non-responders and therefore treated as a failure (e.g. no DAS28(CRP) remission or no moderate/good EULAR response). Imputation rules for each case are described in section 4.5.2:

A dataset will be created with these imputation rules and will be referred to as the NRI dataset. The NRI dataset will be the primary dataset used for all binary efficacy endpoints. Imputed response for each binary endpoint will be presented by visit and subject in listings.

For the efficacy evaluations of continuous endpoints, results recorded for subjects who received rescue treatment or exceeded 10 mg/day prednisone equivalent oral corticosteroids, subjects with any new use of parenteral corticosteroids, more than one intra-articular corticosteroid injection within a 24 week period, or subjects who received rescue treatment will be set to missing at the same visits that were set to non-responder for the binary endpoints. This is a change from protocol section 9.3.2. A dataset will be created and will be referred to as the Set-to-Missing (STM) dataset.

For safety endpoints, no imputation for missing data will be done.

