## 4.5.2 Missing Data for Efficacy and Safety Endpoints

### 4.5.2.1 Missing Data for Efficacy Endpoints

Missing visit data for each efficacy endpoint will be handled as described in Sections 3.2 and 4.3.1. For each continuous endpoint, change from baseline will be missing at visits with missing post-baseline values or where data were imputed to missing.

For the binary endpoints, subjects with missing efficacy data, early withdrawals, subjects who exceed the allowed dose of corticosteroid, who received new parenteral corticosteroids or more than one intra-articular corticosteroid injection within a 24 week period, or subjects who received rescue treatment will be imputed as non-responders and therefore treated as a failure (e.g. no DAS28(CRP) remission or no moderate/good EULAR response).

For subjects who exceed the allowed dose of corticosteroid, who received new parenteral corticosteroids or more than one intra-articular corticosteroid injection within 24 weeks or subjects who received rescue treatment, continuous efficacy endpoints will be set to missing.

- Missing efficacy data: visits with missing data (due to a missed visit or missing component of a composite endpoint) should be set to treatment failure.
- Early withdrawals (including subjects that are withdrawn at Week 36 due to lack of EULAR response): only visits following the early withdrawal visit should be set to treatment failure.
- Prednisone equivalent >10 mg/day: the visit after a period (time from previous visit up to the day before the current visit) of average daily corticosteroid use exceeding 10 mg/day prednisone and all following visits should be set to treatment failure (continuous endpoints will be set to missing).
- Parenteral corticosteroids: all visits after a subject received any new parenteral corticosteroids (e.g. intravenous and intra-muscular) should be set to treatment failure (continuous endpoints will be set to missing).
- Intra-articular corticosteroids: all visits after the second intra-articular corticosteroid injection within a 24 week period should be set to treatment failure (continuous endpoints will be set to missing).
- Rescue: subjects who rescue to 180 mg dose at Week 14 or 26 should be set to treatment failure at that visit and all subsequent visits (continuous endpoints will be set to missing).

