For binary endpoints with repeated measures over time, Generalized Estimating Equations (GEE) methodology will be used to take correlation among subject-level responses over time into account. The model will include data from all assessment points from Week 1 to Week 62. Due to only few expected subjects with remission in some randomised treatment groups (especially placebo) only standard errors and resulting confidence intervals will be adjusted. To this end an independent working correlation structure will be assumed and standard errors will be calculated based on the empirical sandwich covariance estimate (default setting for PROC GENMOD in SAS) (Stokes, Davis, & Koch, 2012).

For the primary analysis of DAS28(CRP) remission at Week 24, the GEE model will include terms for randomised treatment group, baseline DAS28(CRP), visit and interaction terms for treatment group-by-visit and baseline-by-visit. A sensitivity analysis including covariates age, gender, weight and disease duration (<2 years,  $\geq 2$  years) will be considered by adding covariate terms to the repeated measures model one at a time along with the covariate-by-treatment group interaction term. If the interaction term is not significant at  $\alpha=0.10$  it will be removed from the model. Likewise, if the covariate term is not significant at  $\alpha=0.10$  it will be removed from the model. Other covariates will be tested in a similar manner.

Survival analyses (time to event analyses) will be conducted for the final analysis using Kaplan-Meier methods, comparing each GSK3196165 dose to placebo. Between-group differences will be analysed using the log-rank statistic. Median time to remission will be presented for each randomised treatment group. Kaplan-Meier plots of the time to remission will be presented. Subjects who withdraw from the study are censored at the time of withdrawal. All other subjects are censored at the end of the study.

In addition to summaries of the individual components of composite endpoints, numbers and percentages of subjects meeting the following criteria will be presented:

- TJC68  $\leq 1$
- SJC66  $\leq 1$
- CRP  $\leq 1\text{mg/dl}$
- PtGA  $\leq 10$
- SDAI  $\leq 3.3$

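### Time to first remission censors subjects withdrawn for non-response, against the SAP's own failure rule, and does not say which remissions count as events or when follow-up stops

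*SAP*

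**What the plan says.** SAP Section 2 lists "Time to first DAS28(CRP) remission" among the major secondary efficacy endpoints. SAP 4.9.2.2 analyses it at the final analysis with Kaplan-Meier curves, medians and a test of each dose against placebo: "Between-group differences will be analysed using the log-rank statistic". The censoring rule is: "Subjects who withdraw from the study are censored at the time of withdrawal. All other subjects are censored at the end of the study".

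Protocol 5.4 states that a subject without a good or moderate EULAR response at Week 36 "will not be dosed at Week 38, and will be withdrawn from the study". This applies in every arm.

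For binary endpoints SAP 4.3.1 says: "The NRI dataset will be the primary dataset used for all binary efficacy endpoints". Under early withdrawals, SAP 4.5.2.1 expressly includes the Week 36 EULAR withdrawals and says that "only visits following the early withdrawal visit should be set to treatment failure". Its rule for escalated subjects reads: "subjects who rescue to 180 mg dose at Week 14 or 26 should be set to treatment failure at that visit and all subsequent visits". The same section sets subjects who breach the corticosteroid limits to failure. SAP 4.9.2.2 has no rule for rescue or steroid failure in the time-to-event analysis, and SAP 4.14 does not mention the endpoint.

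**The concern.** Kaplan-Meier and the log-rank test assume that a censored subject has the same future chance of remission as those still under observation. A subject withdrawn at Week 38 has just been identified as a non-responder, yet is treated as if likely to remit at the rate of the responders who stayed. The by-visit remission analysis calls the same subject a failure. One SAP thus handles the same people in two ways on the same variable.

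A second gap sits beside this. The censoring rule keeps rescued subjects at risk in their randomised arm, but the section does not say whether a remission reached on the escape dose is an event there. It also gives no week for the end of the study. SAP 4.2 defines a subject's end of study as the last available assessment on or after the last treatment. The design schema shows local standard of care after Week 52, and efficacy summaries run to Week 62. At stake are the curves, the medians and, on one reading, the comparison with placebo itself.

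**Working it through.** **The plan's own figures.** The documents give no event count, power or median for this endpoint. Their nearest figure is power for Week 24 remission (33% against 3%, 35 per arm, Fisher's exact test, two-sided 0.05). Exact enumeration gives 90.9% against the stated 90% or so, but this says nothing about time to first remission.

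**The rules side by side.**

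| Subject | By-visit remission (SAP 4.5.2.1) | Time to first remission (SAP 4.9.2.2) |
|---|---|---|
| Withdrawn at Week 38 for no EULAR response | failure at later visits | censored at withdrawal |
| Other early withdrawal | failure at later visits | censored at withdrawal |
| Rescued at Week 14 or 26 | failure from that visit | at risk to study end; event source not stated |
| Steroid failure, still on study | failure from the relevant visit | at risk to study end; event source not stated |

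The first two rows conflict with no assumption needed. The last two are unspecified.

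**Hand calculation for the mandated withdrawals.** Let F be the fraction in remission by Week 38, S = 1 − F, w the fraction of the arm withdrawn then, and h the later remission risk among those who stay.

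- Kaplan-Meier: 1 − S(1 − h)
- Failures kept in the denominator: F + (S − w)h
- Difference: w × h

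With F = 0.30 (assumed), w = 0.05 and h = 0.10, this is 0.370 against 0.365. With w = 0.30 and h = 0.20 it is 0.440 against 0.380. Over w of 5–30% and h of 5–20%, the excess runs from 0.3 to 6 points.

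**Simulation for size.** From the SAP: Week 12 changes of −1.0 (placebo), −2.1 (90 mg) and −2.32 (180 mg), SD 1, the escape rules and the Week 36 rule. Assumed, not in the documents: baseline DAS28 mean 5.8 (SD 0.8), a 6-week onset constant, 50–85% of variance between subjects, a full move to the 180 mg response after escape, and random dropout by Week 52.

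- *Mandated withdrawals alone, no other dropout.* They affect 3.8–6.6% of subjects. The largest excess at Week 52 is 1.6 points (56.5% against 54.9%, placebo, post-rescue remissions counted). With NRI-derived remission the largest is 0.6 points (69.0% against 68.4%, 180 mg).
- *All withdrawals, 15% dropout.* Week 52 cumulative remission:

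| Arm | SAP censoring, NRI remission | Withdrawals kept event-free, NRI remission | SAP censoring, post-rescue remissions counted |
|---|---|---|---|
| Placebo | 12% | 11% | 49% |
| 90 mg | 43.8% | 41.5% | 56.1% |
| 180 mg | 60.2% | 56.4% | 60.2% |

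The first two columns differ by about 1, 2.3 and 3.8 points. At 25% dropout the differences are 1.1, 3.8 and 6.2.

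- *Log-rank power, 35 per arm.* With NRI remission, SAP censoring gives 98.9% for 180 mg and 86.6% for 90 mg. Keeping withdrawals event-free gives 98.8% and 86.4%. With post-rescue remissions counted, power falls to about 41% and 25%.

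**Why the event source matters so much.** Take a placebo change of −1.1 at Week 24 (assumed), SD 1, and baseline mean 5.4–6.2 with SD 0.8 (assumed), independent of the change. Week 24 DAS28 then has mean 4.3–5.1 and SD √(0.64 + 1) = 1.28. The chance of exceeding 3.2 is Φ(1.1/1.28) = 81% to Φ(1.9/1.28) = 93%. Most late remissions in the placebo arm would then occur on the escape dose.

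**Error rate under identical responses, 180 mg against placebo** (2,000 trials each; Monte Carlo SE about 0.5 points at 5%). The log-rank test rejects in 6.0–7.8% of trials with SAP censoring and NRI remission, and in 6.7–7.9% with withdrawals kept event-free. The cause is that 180 mg has no escape, so only placebo subjects lose later events.

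**The case against.** The best reply is that the SAP already points to NRI-derived remission. Table 6 places the survival analysis in the DAS28(CRP) remission row, SAP 4.3.1 makes NRI primary for every binary endpoint, and SAP 3.2.1 treats a missing score as no remission. On that reading a rescued subject stays at risk with no later event, which is the NRI rule itself. This stands. A reader might infer that keeping rescued subjects at risk to study end is biased or contradicts NRI. The documents do not support that unless observed post-rescue remissions are counted, which the SAP neither says nor excludes.

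A reader might also construct a large withdrawal effect: 35 subjects, 10 remitting by Week 36, 12 withdrawn at Week 38 and 3 of the other 13 remitting later. This gives 1 − (25/35)(10/13) = 45% against 13/35 = 37%. The arithmetic is right, but nothing in the documents supports withdrawing 34% of an arm; the simulation gives 4–7%. Nor is the inflation greatest in the weakest arms: with NRI remission it is smallest for placebo, where few later events remain to lend to censored subjects.

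Finally, this is one secondary endpoint without multiplicity control, and by-visit NRI remission differences are reported through Week 52 anyway. That limits the consequence. It does not remove the conflict on withdrawals, which holds even on the NRI reading.

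**Conclusion.** The concern holds in two parts.

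First, censoring at withdrawal is outcome-dependent for the mandated Week 38 withdrawals and conflicts with the failure rule in SAP 4.5.2.1. Its effect is modest: about 1–4 points at Week 52 for all withdrawals under 15% dropout with NRI remission, at most 1.6 points for the mandated ones alone, and almost none on the log-rank test. It would be wrong to conclude that the medians and p-values cannot be interpreted.

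Second, the event dataset and the cut-off week are missing. This is a gap in specification, not a demonstrated bias, but one permissible reading would take placebo from about 12% to about 49% and power for 180 mg from 99% to about 41%.

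The conflict in the text rests on no assumption. The sizes rest on the assumed baseline, onset, variance split, post-escape response and dropout. The primary Week 24 analysis and the interim rules do not use this endpoint.

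**What to change.** Amend SAP 4.9.2.2 before unblinding, and record the change in 4.14:

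- The event is the first visit up to Week 52 with remission in the NRI dataset. Remissions after rescue or steroid failure are then not events.
- Withdrawn, rescued and steroid-failure subjects without an earlier event stay event-free to Week 52. At minimum this covers those withdrawn for lack of EULAR response. Extending it to administrative withdrawals is a choice of estimand and should be stated as such.
- Curves, medians and log-rank tests use this definition. Censoring at withdrawal becomes a sensitivity analysis.

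Censoring at rescue is not a remedy: it too is driven by outcome, and in the simulation it puts placebo at about 51% by Week 52.

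The cost is a few sentences and the reprogramming of one endpoint. The curves will be slightly lower. Because 180 mg has no escape, the coding slightly favours 180 mg over placebo (about 6–8% rejection under identical responses). The existing rule with NRI remission shares this feature, and the report should disclose it.

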#### **4.9.3 Exploratory Efficacy Endpoints**

Exploratory efficacy endpoints will only be analysed at the final analysis.

##### **4.9.3.1 Proportion of subjects achieving sustained ( $\geq 24$ continuous weeks including the Week 52 visit) DAS28(CRP) remission**

Proportion of subjects achieving sustained remission will be analysed and summarised as described in section 4.9.2 for DAS28(CRP) remission, but without using any GEE methods..

The duration of sustained DAS28(CRP) remission will be summarised.

##### **4.9.3.2 Proportion of subjects achieving Major Clinical Response (ACR70 for $\geq 24$ continuous weeks including the Week 52 visit)**

Proportion of subjects achieving major clinical response as described in section 3.2.2 will be analysed and summarised in the same way as described in section 4.9.2.2 for DAS28(CRP) remission, but without using any GEE methods.

#### **4.9.3.3 DAS28(ESR) scores/responses at all assessment timepoints.**

DAS28(ESR) scores will be summarised by EULAR response (moderate/good response and no response), observed values, change from Baseline and remission (DAS28(ESR)<2.6) at all assessment points.

### **4.10 Safety Evaluation**

All safety summaries and analyses will be based upon the ITT population by actual treatment group at the time of safety event or assessment. Actual treatment group is either the randomised treatment group or “Rescued Subjects” for subjects who got escalated. Only assessments that happen after the administration of the first dose of rescue treatment will be assigned to the treatment group of “Rescued Subjects”.

#### **4.10.1 Extent of Exposure**

The extent of exposure to GSK3196165 will be evaluated by summarizing the number of injections, the amount of study medication received in mg and the duration of drug exposure in days. Exposure to GSK3196165 will be summarised by time period (Overall, Day 1 to <Week 14, Week 14 to <Week 26, Week 26 to <Week 38, and Week 38 to <Week 52).

Duration of drug exposure will be calculated as:

- date of the last injection during study – date of first injection during study + 1 day

Weekly MTX dose will be averaged across the entire study and within each time period for each subject.

MTX dose should be documented in mg, but in case ml is captured the following conversion should be used: 1ml is equivalent to 25mg.

A contingency table will be created for Week 12 and Week 24 showing the number of subjects that were escalated/not escalated correctly/falsely. For Week 36 a corresponding table will be created showing correct and false withdrawals due to lack of EULAR good/moderate response.

Overall Extent of exposure and extent of exposure by time period will also be presented in by-subject listings.

#### **4.10.2 Adverse Events**

AEs will be coded using the MedDRA in the latest available version.

Treatment emergent AEs (TEAE) are defined as AEs starting on or after the first administration of study medication and up to 12 weeks after last dose of study medication. AEs that are not treatment emergent are defined as pre-treatment AEs or post-treatment AEs, respectively.

Adverse events of special interest (AESI) will be derived using Common Terminology Criteria for Adverse Events, 2009 v4.0 (CTCAE) and will include:

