
Potential Risk of Clinical Significance	Summary of Data/Rationale for Risk	Mitigation Strategy
Pulmonary alveolar proteinosis (PAP)	
GM-CSF signalling is required to maintain the normal function of alveolar macrophages. Long-term absence of GM-CSF signalling (e.g., via hereditary GM-CSF deficiency or development of anti-GM-CSF auto-antibodies) is known to cause the extremely rare condition of PAP, which is characterized by the accumulation of surfactant lipids and protein in the alveolar spaces, with resultant impairment in gas exchange.
 
Non-clinical Data: Non-adverse minimal to mild foamy alveolar macrophage accumulation were noted in lungs of monkeys in the 13-week SC and 26-week IV toxicology studies, but reversible following off drug period. Dose levels at which foamy alveolar macrophages were not observed were identified in these studies.
 
Clinical Data: No cases of PAP have been reported to date in the clinical development program. Furthermore evaluation of pulmonary function has not demonstrated any abnormalities in pulmonary functions.
	
study.
 
Subject selection (see Section 5.1):
 
 
Subjects with history of clinically-significant respiratory diseases that required treatment and/or follow up, or chronic cough or dyspnea will not be permitted to enter the study.
 
Pulmonary function testing (spirometry, <math>D_{LCO}</math>) measurements will be performed at baseline in order to exclude those subjects with moderate-severe impairment.
 
 
Dose Duration:
 
 
The exposure duration to GSK3196165 in this study is 12 months. Although the time course of PAP development in humans is unknown, the published literature suggests that it requires full inhibition of GM-CSF for years before clinical manifestation of the disease can be detected (refer to IB GSK Document Number [2014N190256_01] for further details). Therefore, the risk of development of PAP in this study is anticipated to be low.
 
 
Subject Monitoring:
 
 
Specific pulmonary assessments are a requirement of the study protocol: 
 
Subjects will be assessed every visit for the development of cough and dyspnea, and will also have regular chest auscultation and pulse oximetry measurements. Persistent cough or dyspnea will be reported as an AESI.
 
Pulmonary function testing (spirometry and <math>D_{LCO}</math> measurements) will be performed at baseline, and then every 3 months during treatment and at the follow-up visit. Relative change in <math>D_{LCO} > 15\%</math> from baseline will be reported as an AESI if confirmed with three consecutive weekly tests.
 
 
 
In the event of clinically-significant pulmonary events, it is recommended
 

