#### **7.4.6. AEs of Special Interest**

Please see Section 4.7.1 for a discussion of potential risks with GSK3196165. Adverse events of special interest include:

- Serious infections, including serious respiratory infections.

- Opportunistic infections including TB reactivation.
- Neutropenia.
- Non life-threatening pulmonary changes related to surfactant accumulation.
- PAP.
- Hypersensitivity reactions, including anaphylaxis.
- Injection site reactions.
- Persistent cough or dyspnea.

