**Table 7 Adverse Events of Special Interest**

AESI	Programmatical Derivation
TP-GDO-WW-016-03 Effective Date: 26 Aug 15 Related to: SOP-GDO-WW-019	CONFIDENTIAL Project Document Version No. 2.0 Project Document Effective Date: Date of last signature Page 56 of 80

Serious infections, including serious respiratory infections.	SAEs, Filter on infections SOC
Opportunistic infections including TB reactivation	Opportunistic infections will be adjudicated by the SRT, using the preferred terms list given in Appendix A . Final adjudication conducted by SRT.
Neutropenia	Based on Grade 3 or 4 absolute neutrophil count
PAP (Pulmonary alveolar proteinosis)	If identified then list all AEs for those subjects.
Hypersensitivity reactions, including anaphylaxis	Hypersensitivity reactions will be adjudicated by the SRT, using AE data and data from hypersensitivity reactions eCRF page. Final adjudication conducted by SRT.
Injection site reactions	Using data from Injection site reactions eCRF page

AEs with missing intensity will be considered severe. AEs with missing relationship to study medication will be considered as related both to GSK3196165/Placebo and to MTX.

Where dates are missing or partially missing, adverse events will be assumed to be treatment-emergent, unless there is clear evidence (through partial dates as described in section 4.5) to suggest that the adverse event started prior to the first dose of study treatment or more than 12 weeks after the last dose of study treatment.

Adverse Events will be summarised by system organ class (SOC) and preferred term (PT). Summaries will provide the number of subjects reporting at least one AE and the total number of events reported.

The following summaries of AEs will be provided by actual treatment group at the time of the AE:

- Overall summary of AEs, including number and percentages of subjects with
  - Any AE
  - Serious AE
  - Discontinuation due to AE
  - Drug-related AE
  - AE leading to death
- Overall summary of Adverse Events
- Number and percentage of subjects reporting an Adverse Events
- Most common AEs (reported by >5% of the subjects in total)
- Plot of Most Common Adverse Events and Relative Risk
- Number and percentage of subjects reporting an Adverse Events by maximum intensity
- Number and percentage of subjects reporting an adverse events by relationship to study treatment

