- Number and percentage of subjects reporting an adverse events of special interest

- Number and percentage of subjects that withdraw from study or discontinue study treatment as result of an adverse event
- Number and percentage of subjects with adverse events during the initial treatment period (up to Week 14 visit)
- Number and percentage of subject reporting an adverse event by study period at the time of the first onset of the adverse events
- Exposure-adjusted (patient years) adverse events by treatment group, where the total number of subjects for each column includes all subjects who took the dose at least once during the study. The exposure-adjusted rate divides the total number of AEs attributed to each dose by duration of exposure (in years) to that dose. The duration for subjects who complete the study on their randomised dose is (date of last dose – date of first dose + 1). For subjects who escape, duration is based on treatment periods defined in Section 4.2.

Exposure adjusted incidence rates are calculated as  $X/T*100$  with

- X being the number of occurrences of the relevant AE for subjects while being in the corresponding treatment group
- T being the cumulative duration of exposure (in years) for subjects in the corresponding treatment group

Adverse event summaries will be ordered by decreasing frequency for SOC, and PT within SOC, summed up for all subjects and then alphabetically for SOC, and PT within SOC.

A by-subject listing of all adverse events will be provided as well as a by-subject listing of all AEs leading to withdrawal from study. These listings will be presented by actual treatment group and will include: center, subject identifier, age, sex, race, weight, adverse event (SOC, PT, and verbatim term), date of onset, date of resolution, duration, intensity, action taken, outcome, relationship to study medication, action taken with study medication, other action taken and whether the AE is treatment-emergent, serious and an AE of interest.

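### SAP Table 7 omits three lung categories that the protocol calls adverse events of special interest, and SAP 4.14 does not declare the difference

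*SAP*

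**What the plan says.** **Protocol.** Section 7.4.6 has eight AESI bullets. Two concern the lung beyond infection and pulmonary alveolar proteinosis (PAP): "Non life-threatening pulmonary changes related to surfactant accumulation" and "Persistent cough or dyspnea". The pulmonary part of the risk table in section 4.7.1 repeats one of them ("Persistent cough or dyspnea will be reported as an AESI") and adds one that 7.4.6 does not carry: a relative DLCO change above 15% "from baseline will be reported as an AESI if confirmed with three consecutive weekly tests". Section 7.4.4.3, on follow-up of events, points to 4.7.1 as the place where AESIs are defined.

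**SAP.** Section 4.10.2 says "Adverse events of special interest (AESI) will be derived using Common Terminology Criteria for Adverse Events, 2009 v4.0 (CTCAE) and will include", followed by Table 7. The table has six rows: serious infections, opportunistic infections, neutropenia, PAP, hypersensitivity reactions and injection site reactions. The same section plans a table described as "Number and percentage of subjects reporting an adverse events of special interest" and an AE listing that flags whether each event is an AE of interest. Section 4.9.1.6 plans an AESI summary for each subgroup.

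Persistent cough, persistent dyspnea and persistent DLCO decrease are handled in SAP 4.10.5, outside Table 7, with final adjudication by the Safety Review Team (SRT). SAP 4.14, the section for changes to the planned analysis, does not mention AESIs.

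**The concern.** The protocol tells investigators which events are of special interest, and its section 9.4.3 names AESIs among the displays on which clinical interpretation of safety will rest. If the SAP programs a shorter list, the study report will contain AESI counts that do not follow the protocol's definition, and a reader will have no statement that the definition changed.

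The categories left out are all pulmonary. Protocol 4.7.3 gives pulmonary toxicity and infection as examples of the key potential risks of blocking GM-CSF. The only non-infectious lung row kept in Table 7 is PAP, which protocol 4.7.1 regards as unlikely to appear within the treatment period of this study. The omitted rows are the milder events that a 52-week trial could more plausibly record. Protocol 2.1.4 reports a numerical imbalance in cough in the previous RA study, 0 of 27 on placebo and 3 of 69 on active treatment, so these categories are not idle ones.

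**Working it through.** No calculation is at issue, so the check compares lists and then traces where each category goes.

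**Step 1. Compare the lists.**

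| Category | Protocol 7.4.6 | Protocol 4.7.1 (pulmonary entry) | SAP Table 7 |
|---|---|---|---|
| Serious infections | yes | – | yes |
| Opportunistic infections | yes | – | yes |
| Neutropenia | yes | – | yes |
| PAP | yes | – | yes |
| Hypersensitivity | yes | – | yes |
| Injection site reactions | yes | – | yes |
| Surfactant-related changes, not life-threatening | yes | not stated | **no** |
| Persistent cough or dyspnea | yes | yes | **no** |
| Confirmed DLCO change >15% | not listed | yes | **no** |

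Count: 8 in protocol 7.4.6 + 1 found only in 4.7.1 = 9. Table 7 has 6, and 9 − 6 = 3. Against 7.4.6 alone the shortfall is 8 − 6 = 2.

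**Step 2. Look for an explanation.** SAP section 1 says the plan is based on protocol version 06. The logged Amendment 07 changes concern the EULAR response table, chest HRCT and references, and do not touch AESIs, so the version gap does not explain the omission. SAP 4.14 covers continuous efficacy data after rescue or excess corticosteroid, sustained remission, major clinical response and the corticosteroid endpoint. Other sections of the SAP flag their own departures from the protocol (4.3.1, 4.11.1). The AESI list is flagged nowhere.

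**Step 3. Trace each omitted category through the outputs.**

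| Output | Cough/dyspnea | DLCO decrease | Surfactant-related changes |
|---|---|---|---|
| AESI table and AE-of-interest flag, SAP 4.10.2 | not derived | not derived | not derived |
| Subgroup AESI summary, SAP 4.9.1.6 | not derived | not derived | not derived |
| Respiratory events by actual treatment group, SAP 4.10.5 | yes | yes | no |
| By-visit summaries, SAP 4.10.9 | cough grade, Borg score | falls >15% | no |
| DRC respiratory summary, SAP 4.10.11.1 | yes | yes | no |

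SAP 4.9.1.6 also plans a subgroup summary of pulmonary findings, but does not define what enters it.

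**Step 4. Check whether 4.10.5 can simply be referenced.** Not yet, for DLCO:
- The event is labelled as a decrease of >15% but defined as one of ≥15%.
- Duration is three consecutive weeks, glossed as 15 or more days. The protocol asks for three consecutive weekly tests. Three weekly tests span 7 + 7 = 14 days between first and last, or 15 calendar days counting both ends. The lengths agree, but the SAP wording sets no number of tests: two low readings 15 days apart could satisfy it and would not satisfy the protocol.
- Protocol 7.4.6 and 4.7.1 disagree on whether a DLCO change is an AESI at all.

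**The case against.** The strongest reply is that this is mainly a matter of labels. Cough, dyspnea and DLCO events are tabulated by treatment group with SRT adjudication, related measures are summarised by visit, and the DRC receives them. That stands. A reader might infer from Table 7 that lung events vanish from the analysis or are hidden from the DRC; SAP 4.10.5, 4.10.9 and 4.10.11.1 show otherwise. Absence from the DRC's AESI summary means little in itself: that pack already puts hypersensitivity and injection site reactions, both in Table 7, in a different display.

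A reader might also infer that a pooled any-AESI count will understate the drug's main suspected risk. The documents do not support that. The overall AE summary in SAP 4.10.2 has no AESI line, and the AESI table is not said to pool categories; if it reports by category, the six listed counts are unaffected. Protocol 4.7.3 does not rank pulmonary toxicity above infection.

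On surfactant-related changes, the protocol gives no working definition, and any such event reported as an AE would still appear in the tables by system organ class and preferred term and in the AE listing. Biomarker analyses are left to a separate plan. These points soften the gap but do not give the category an AESI count.

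Finally, the lead-in to Table 7 could be read as non-exhaustive. That does not help a programmer, who has derivations for six categories and none for the other three.

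**Conclusion.** The mismatch holds and is wrong as written. Three of nine protocol AESI categories are absent from the SAP's AESI derivation, all of them pulmonary, and the change is not declared. If only protocol 7.4.6 is counted, it is two of eight. The outputs affected are the AESI incidence table, the AE-of-interest listing flag and the subgroup AESI summary.

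The consequence is limited. For cough, dyspnea and DLCO decrease the inconsistency is in the AESI classification, not in the reporting of the data. For surfactant-related changes there is a true gap: no dedicated derivation or output. No size of undercount can be given, because the documents state no expected rates for these events.

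This rests on two assumptions: that Table 7 is programmed as it stands, and that 4.7.1 helps define AESIs, which protocol 7.4.4.3 supports.

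**What to change.** 1. Reconcile the sources first. Align the label and definition of the DLCO event in SAP 4.10.5 (>15% against ≥15%), align its 15-or-more-days rule with the protocol's three consecutive weekly tests, and make protocol 7.4.6 and 4.7.1 agree on whether a confirmed DLCO change is an AESI.
2. Add three rows to SAP Table 7: persistent cough or dyspnea and confirmed DLCO change, both by cross-reference to the reconciled 4.10.5, and surfactant-related changes. For the last, state how cases will be identified, for example by SRT adjudication of reported AEs.
3. Confirm that the three rows feed the AESI table and listing flag in 4.10.2 and the subgroup AESI summary in 4.9.1.6.
4. Leave the DRC pack as it is; it already has the cough, dyspnea and DLCO summary.

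If the sponsor prefers to keep six categories, the departure should be declared and justified in SAP 4.14.

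The cost is SAP wording, a few table rows and a clarification between two protocol sections. The cough, dyspnea and DLCO data are already collected. The documents name no data source for surfactant-related changes, so that rule needs a decision; adjudicating reported AEs would use data already in hand.
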